10.7. Appendix 7: Substudy A

10.7.1. Substudy Summary

10.7.1.1. Synopsis

See Section 1.1 for a synopsis of Substudy A.

10.7.1.2. Schema

| | Visit Number | 1 | 2 | 3 | 4 | Unplanned |
|---|------------------|-------------|-----------|-----------|-----------|---------------|
| | Visit | Booster | 1-Month | 6-Month | 12-Month | Potential |
| | Description | Vaccination | Telephone | Follow-Up | Telephone | COVID-19 |
| | | | Contact | Visit | Contact | Illness Visit |
| Participants having received 2 prior doses of 30 µg BNT162b2 at least | Group 1 (n=5000) | BNT162b2 | | | | |
| 6 months prior to randomization | Group 2 (n=5000) | Placebo | | | | |
| | Blood draw | 20 mL | | 20 mL | | |

| Visit Number | 101 | 102 | 103 | Unplanned |
|----------------------|-------------------------|--------------------------------|------------------------------|-------------------------------------|
| Visit Description | BNT162b2 Vaccination | 1-Month Telephone Contact 2 | 6-Month Telephone Contact | Potential COVID-19 Illness Visit |
| Group 2 | BNT162b2 | | | |
| Blood Draw | 20 mL | | | |

10.7.1.3. Schedule of Activities for Substudy A

| Visit Number | 1 | 2 | 3 | 4 | Unplanned |
|--|------------------------|---------------------------------|--|---|--|
| Visit Description | Booster Vaccination | 1-Month Telephone Contact | 6-Month Follow-Up Visit ^a | 12-Month Telephone Contact ^a | Potential COVID-19 Illness Visit ^b |
| Visit Window | Day 1 ^c | 28 to 35 Days After Visit 1 | 175 to 189 Days After Visit 1 | 350 to 378 Days After Visit 1 | Optimally Within 3 Days After Potential COVID-19 Illness Onset |
| Obtain informed consent | X | | | | |
| Obtain the participant's prior participant number from Study C4591001 | X | | | | |
| Assign participant number | X | | | | |
| Obtain demography and medical history data | X | | | | |
| Perform clinical assessment ^d | X | | | | |
| For participants who are HIV-positive, record latest CD4 count and HIV viral load | X | X | X | X | |
| Measure height and weight | X | | | | |
| Measure temperature (body) | X | | | | |
| Perform urine pregnancy test (if appropriate) | X | | | | |
| Confirm use of contraceptives (if appropriate) | X | X | | | |
| Collect nonstudy vaccine information | X | X | | | |
| Collect prohibited medication use | | X | X | X | X |
| Confirm eligibility | X | | | | |
| Review temporary delay criteria | X | | | | |
| Collect blood sample for immunogenicity assessment | ~20 mL | | ~20 mL | | |
| Obtain nasal (midturbinate) swab | X | | | | X |
| Obtain randomization number and study intervention allocation | X | | | | |
| Administer study intervention | X | | | | |
| Assess acute reactions for at least 30 minutes after study intervention administration | X | | | | |
| Explain participant communication methods, assist the participant with downloading the app, or issue provisioned device, if required | X | | | | |

| Visit Number | 1 | 2 | 3 | 4 | Unplanned |
|--|------------------------|---------------------------------|--|---|--|
| Visit Description | Booster Vaccination | 1-Month Telephone Contact | 6-Month Follow-Up Visit ^a | 12-Month Telephone Contact ^a | Potential COVID-19 Illness Visit ^b |
| Visit Window | Day 1 ^c | 28 to 35 Days After Visit 1 | 175 to 189 Days After Visit 1 | 350 to 378 Days After Visit 1 | Optimally Within 3 Days After Potential COVID-19 Illness Onset |
| Provide/ensure the participant has a thermometer | X | | | | |
| Request the participant return the e-diary or assist the participant to delete the application | | | | X | |
| Collect AEs and SAEs as appropriate | X | X | Xe | | Xf |
| Collection of COVID-19-related clinical and laboratory information (including local diagnosis) | | | | | X |
| Contact the participant by telephone | | X | | X | |

- a. This visit will be conducted for all participants if the study remains blinded at the time of the visit or, if the study has been unblinded, for participants who originally received BNT162b2 or placebo recipients who declined BNT162b2 booster vaccination.
- b. The COVID-19 illness visit may be conducted as an in-person or telehealth visit.
- c. The visit may be conducted across 2 consecutive days; if so, all steps from assessing the inclusion and exclusion criteria onwards must be conducted on the same day.
- d. Including, if indicated, a physical examination.
- e. Any AEs occurring up to 48 hours after the blood draw must be recorded (see Section 8.3.1).
- f. AEs need only be recorded if the participant remains in the AE reporting period (see Section 8.3.1).

10.7.1.3.1. Administration of BNT162b2 to Those Originally Assigned to Placebo

Participants who originally received placebo will have the opportunity to receive BNT162b2 as part of the study either indicated by, and at a time informed by, the outcome of the interim analyses detailed in Section 10.7.9.4 or at a time decided at the discretion of the sponsor.

| Visit Number | 101 | 102 | 103 | Unplanned |
|--|---|----------------------------------|------------------------------------|---|
| Visit Description | BNT162b2 Vaccination | 1-Month Telephone Contact 2 | 6-Month Telephone Contact | Potential COVID-19 Illness Visit |
| Visit Window | As Informed by the Outcome of the Interim Analyses, or at the Discretion of the Sponsor | 28 to 35 Days After Visit 101 | 175 to 189 Days After Visit 101 | Optimally Within 3 Days After Potential COVID-19 Illness Onset |
| Confirm participant originally received placebo | X | | | |
| For participants who are HIV-positive, record latest CD4 count and HIV viral load | X | X | X | |
| Perform urine pregnancy test (if appropriate) | X | | | |
| Confirm use of contraceptives (if appropriate) | X | | | |
| Collect prohibited medication use | X | X | X | X |
| Confirm eligibility | X | | | |
| Review temporary delay criteria | X | | | |
| Collect blood sample for immunogenicity assessment | ~20 mL | | | |
| Obtain nasal (midturbinate) swab | X | | | X |
| Obtain vaccine vial allocation via IRT | X | | | |
| Administer BNT162b2 | X | | | |
| Assess acute reactions for at least 30 minutes after study intervention administration | X | | | |
| Request the participant return the e-diary or assist the participant to delete the application | | | X | |
| Collect AEs and SAEs as appropriate | X | X | X | X ^a |
| Collection of COVID-19–related clinical and laboratory information (including local diagnosis) | | | | X |
| Contact the participant by telephone | | X | X | |

Abbreviations: HIV = human immunodeficiency virus; IRT = interactive response technology.

a. AEs need only be recorded if the participant remains in the AE reporting period (see Section 8.3.1).

10.7.2. Introduction

10.7.2.1. Study Rationale

Substudy A will evaluate the safety, tolerability, and efficacy of a booster dose of BNT162b2 when administered to participants having previously received 2 doses of BNT162b2 at least 6 months prior to randomization.

10.7.2.2. Background

See Section 2.2 for the study background.

10.7.2.3. Benefit/Risk Assessment

No additional risks are identified for Substudy A beyond those detailed for the master study (see Section 2.3).

10.7.2.3.1. Benefit Assessment

Benefits to individual participants enrolled in Substudy A may be:

- Receipt of a booster dose of an efficacious or potentially efficacious COVID-19 vaccine that may convey a longer duration of protection during a global pandemic.
- Access to COVID-19 diagnostic testing.
- Contributing to research to help others in a time of global pandemic.

10.7.3. Objectives, Estimands, and Endpoints

| Objectives | Estimands | Endpoints |
|--|---|--|
| Primary Efficacy | Primary Efficacy | Primary Efficacy |
| To describe the efficacy of a booster dose of BNT162b2 against confirmed COVID-19 occurring from 7 days after the booster dose through the blinded follow-up period in participants without evidence of past SARS-CoV-2 infection | In participants complying with the key protocol criteria (evaluable participants) and with no serological or virological evidence (prior to 7 days after receipt of the booster dose) of past SARS-CoV-2 infection: 100 × (1 – IRR) [ratio of active vaccine to placebo] | Confirmed COVID-19 incidence from 7 days after the booster dose per 1000 person-years of blinded follow-up |
| To describe the efficacy of a booster dose of BNT162b2 against confirmed COVID-19 occurring from 7 days after the booster dose through the blinded follow-up period in participants with and without evidence of past SARS-CoV-2 infection | In participants complying with the key protocol criteria (evaluable participants) with or without serological or virological evidence (prior to 7 days after receipt of the booster dose) of past SARS-CoV-2 infection: 100 × (1 – IRR) [ratio of active vaccine to placebo] | Confirmed COVID-19 incidence from 7 days after the booster dose per 1000 person-years of blinded follow-up |

| Primary Safety In participants receiving 1 dose of study | Primary Safety |
|---|---|
| In participants receiving 1 dose of study | |
| intervention, the percentage of participants reporting: AEs from the booster dose to 1 month after the booster dose SAEs from the booster dose to 6 months after the booster dose | AEsSAEs |
| Secondary Efficacy | Secondary Efficacy |
| In participants complying with the key protocol criteria (evaluable participants) and with no serological or virological evidence (prior to 7 days after receipt of the booster dose) of past SARS-CoV-2 infection: 100 × (1 – IRR) [ratio of active vaccine to placebo] | Confirmed severe COVID-19 (based on FDA definition) incidence from 7 days after the booster dose per 1000 person-years of blinded follow-up |
| In participants complying with the key protocol criteria (evaluable participants) and with or without serological or virological evidence (prior to 7 days after receipt of the booster dose) of past SARS-CoV-2 infection: 100 × (1 – IRR) [ratio of active vaccine to placebo] | Confirmed severe COVID-19 (based on FDA definition) incidence from 7 days after the booster dose per 1000 person-years of blinded follow-up |
| In participants complying with the key protocol criteria (evaluable participants) and with no serological or virological evidence (prior to 7 days after receipt of the booster dose) of past SARS-CoV-2 infection: 100 × (1 – IRR) [ratio of active vaccine to placebo] | Confirmed severe COVID-19 (based on CDC definition) incidence from 7 days after the booster dose per 1000 person-years of blinded follow-up |
| In participants complying with the key protocol criteria (evaluable participants) and with or without serological or virological evidence (prior to 7 days after receipt of the booster dose) of past SARS-CoV-2 infection: 100 × (1 – IRR) [ratio of active vaccine to placebo] | Confirmed severe COVID-19 (based on CDC definition) incidence from 7 days after the booster dose per 1000 person-years of blinded follow-up |
| | Cf1 COVID 10 |
| booster vaccination (at initial randomization or subsequently): | Confirmed COVID-19 incidence per 1000 person-years of follow-up |
| | reporting: AEs from the booster dose to 1 month after the booster dose SAEs from the booster dose to 6 months after the booster dose Secondary Efficacy In participants complying with the key protocol criteria (evaluable participants) and with no serological or virological evidence (prior to 7 days after receipt of the booster dose) of past SARS-CoV-2 infection: 100 × (1 – IRR) [ratio of active vaccine to placebo] In participants complying with the key protocol criteria (evaluable participants) and with or without serological or virological evidence (prior to 7 days after receipt of the booster dose) of past SARS-CoV-2 infection: 100 × (1 – IRR) [ratio of active vaccine to placebo] In participants complying with the key protocol criteria (evaluable participants) and with no serological or virological evidence (prior to 7 days after receipt of the booster dose) of past SARS-CoV-2 infection: 100 × (1 – IRR) [ratio of active vaccine to placebo] In participants complying with the key protocol criteria (evaluable participants) and with or without serological or virological evidence (prior to 7 days after receipt of the booster dose) of past SARS-CoV-2 infection: 100 × (1 – IRR) [ratio of active vaccine to placebo] In participants complying with the key protocol criteria (evaluable participants) and with or without serological or virological evidence (prior to 7 days after receipt of the booster dose) of past SARS-CoV-2 infection: 100 × (1 – IRR) [ratio of active vaccine to placebo] Exploratory In participants who received BNT162b2 at the booster vaccination (at initial randomization or |

10.7.4. Study Design

10.7.4.1. Overall Design

This is a Phase 3 randomized, placebo-controlled, observer-blind substudy to evaluate the safety, tolerability, and efficacy of a booster dose of BNT162b2. Participants \geq 16 years of age who have completed a 2-dose primary series of BNT162b2 at least 6 months prior to randomization will be enrolled, and participants will be randomized at a ratio of 1:1 to receive either BNT162b2 or placebo as shown in Section 10.7.1.2. Randomization will be stratified by age, such that approximately 60% of participants enrolled will be \geq 16 to 55 years of age and approximately 40% of participants >55 years of age. Approximately 10,000 participants will be randomized in the study. Assuming a 15% nonevaluable rate, there will be approximately 4250 evaluable participants in each group.

Participants who are randomized to receive placebo at the booster vaccination visit will be offered the opportunity to receive BNT162b2 if indicated by the outcome of the interim analyses, as outlined below in Section 10.7.4.2.1 and further detailed in Section 10.7.9.4, or at the discretion of the sponsor. The timing of this booster vaccination may be informed by the outcome of the interim analyses detailed in Section 10.7.9.4 or at a time decided by the sponsor.

The study may be terminated early, for reasons including (but not limited to) access to and availability of BNT162b2 in the real world, reducing the value of participant involvement and observation in this clinical trial. Further to this, participants who are offered the possibility to participate in a future study within the Pfizer/BioNTech COVID-19 vaccine development program will be discontinued from this study.

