This is a randomized, observer-blinded substudy to evaluate the safety, tolerability, and immunogenicity of a booster (third) dose of BNT162b2 at 10 µg and at 30 µg. Participants ≥12 years of age who have completed a 2-dose primary series of BNT162b2 (30-µg doses) at least 5 months (150 days) prior to randomization will be enrolled. Participants will be randomized at a ratio of 1:1 to receive BNT162b2 at either a 10-µg or 30-µg dose level at Visit 301. Randomization will be stratified by age with escalation to each higher age group guided by immunogenicity results at 7 days after the third dose. A DMC will review safety (e-diary and AE) and immunogenicity data in the first approximately 100 participants with available immunogenicity (~50 participants in each dose level) 7 days after the third dose. Upon confirmation of an acceptable safety and immunogenicity assessment by the DMC, progression of the next age group will occur independently.

As part of Protocol Amendment 11, progression beyond the 12 through 17 years age group will not occur and no further participants will be enrolled. The rationale for this amendment is that a third dose of COVID-19 vaccine has been recommended for all age groups for a considerable period of time (hence the potential substrate for enrollment is essentially nonexistent) and, for Fall 2022, the recommended booster vaccine will switch to a bivalent original/Omicron-modified vaccine. Both factors contribute to age escalation being operationally unfeasible. Furthermore, since the 30-µg dose level is well tolerated, and in the

face of emergence of SARS-CoV-2 Omicron sublineages for which a maximum immune response is desirable, the rationale for a reduced dose level no longer holds.

Substudy D Design

This is a randomized substudy composed of open-labeled and observer-blinded groups to evaluate the safety, tolerability, and immunogenicity of a 2-dose primary series of BNT162b2 OMI, and as a booster (third or fourth or fifth) dose at investigator sites in the US and South Africa only. Participants ≥18 years of age to ≤55 years of age will be enrolled. Approximately 1420 participants will be enrolled in the study.

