Participants in Cohort 1 will have completed a 2-dose primary series of BNT162b2 (30-µg doses), with their last dose 90 to 240 days prior to enrollment. Approximately 615 participants will be randomized at a ratio of 1:1:1 either to receive 1 dose (third) of BNT162b2 OMI, 2 doses (third and fourth) of BNT162b2 OMI, 4 weeks apart, or 1 dose (third) of BNT162b2. Randomization will be stratified by age (stratified as 18-30 and 31-55 years of age). Participants in Cohort 1 will remain blinded to whether they will be receiving a fourth dose through 1 month after their first dose, but the investigator and sponsor will not be blinded.

Participants in Cohort 2 will be enrolled from Study C4591001 and C4591031 Substudy A and will have completed a 2-dose primary series and received a single booster (third) dose of BNT162b2, with their last dose 90 to 180 days prior to randomization. Approximately 600 participants will be randomized at a ratio of 1:1 to receive a fourth dose of either BNT162b2 or BNT162b2 OMI at Visit 401. Participants will be offered a dose of BNT162b2 OMI at Visit 404 (3-month follow-up). Randomization will be stratified by age (stratified as 18-30 and 31-55 years of age). Cohort 2 will be observer-blinded.

In Cohort 3, 205 participants 18 through 55 years of age who are COVID-19 vaccine—naïve and have not experienced COVID-19 will be enrolled to receive 2 doses (primary series) of BNT162b2 OMI, 3 weeks apart, with a dose of BNT162b2 approximately 5 months (150 days) later. If participants do not consent to receive BNT162b2 as a third dose, they will not receive a third dose. No participants should receive BNT162b2 OMI as a third dose.

Table 1 details the number of participants by cohort and group, their prior BNT162b2 experience, the vaccine that will be administered, and the number of doses administered as part of Substudy D.

Table 1. Total Number of Participants by Cohort

| Cohort | Group | Prior BNT162b2 Experience | Vaccine | Number of Doses Administered as Part of Substudy D | Total Number of Participants |
|----------|----------|---------------------------------|--------------|---|---------------------------------|
| Cohort 1 | Group 1 | 2 Doses | BNT162b2 OMI | 1 | 205 |
| | Group 2 | 2 Doses | BNT162b2 OMI | 2 | 205 |
| | Group 2b | 2 Doses | BNT162b2 | 1 | 205 |

| Table 1. I dial Number of Latticipants by Conor | Table 1. | Total Number of Participants by Cohort |
|---|----------|---|
|---|----------|---|

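### Substudy A discontinues anyone merely offered a later program study, so participants who decline lose 6-month SAE follow-up; the effect is modest and the wording is easily mended

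*Protocol*

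**What the plan says.** Protocol Section 10.7.4.1, in the paragraph on early termination of Substudy A, says that "participants who are offered the possibility to participate in a future study within the Pfizer/BioNTech COVID-19 vaccine development program will be discontinued" from the substudy. Section 1.1 repeats the rule in the same words.

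For Substudy D, Section 1.1 says: "Participants in Cohort 2 will be enrolled from Study C4591001 and C4591031 Substudy A". These people have had a third dose, "with their last dose 90 to 180 days prior to randomization". On size: "Approximately 600 participants will be randomized at a ratio of 1:1 to receive a fourth dose". On age: "Participants ≥18 years of age to ≤55 years of age will be enrolled". The split of Cohort 2 between its two source studies is not given.

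The SAE part of Substudy A's primary safety estimand (Section 10.7.3) is "SAEs from the booster dose to 6 months after the booster dose". The contact that closes this period is Visit 3, at "175 to 189 Days After Visit 1" (Section 10.7.1.3). For placebo recipients who later receive BNT162b2 at Visit 101, it is Visit 103, at the same interval after Visit 101 (Section 10.7.1.3.1). Section 8.3.1 sets SAE collection for all participants at about 6 months after each vaccination.

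**The concern.** The rule takes effect on something the sponsor does, not on a choice the participant makes. A person who is offered Cohort 2 and turns it down is still discontinued from Substudy A, and the text at hand has no provision to pick that person up again:

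- The 6-month telephone contact in Section 7.1 is for people who stop study intervention but remain in the study.
- Once participation has ended, Section 8.3.1 no longer obliges investigators to seek SAEs actively. They must report only SAEs they happen to learn of and consider related.
- The reasons for leaving the study listed in Section 7.2 do not include an offer of another study.

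For a decliner, the discontinuation rule and the 6-month SAE collection cannot both be carried out. At stake is the completeness of the SAE part of a primary objective in boosted participants aged 18 to 55. An SAP cannot repair this, because the data would not have been collected.

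**Working it through.** **Inputs.** Cohort 2 window: days 90 to 180 after the third dose; size about 600 (Section 1.1). 6-month contact: days 175 to 189 (Sections 10.7.1.3 and 10.7.1.3.1). Group size: 5000 (Section 10.7.1.2). Detection probabilities: Table 7 (Section 10.7.9.5).

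**1. The plan's own figure.** P(at least one event) = 1 − (1 − p)^n. With n = 5000 and p = 0.01%, 0.05% and 0.1%, this gives 0.3935, 0.9180 and 0.9933. Table 7 prints 0.39, 0.92 and 0.99, so it is reproduced.

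**2. Overlap of the windows.** Days 90 to 180 inclusive are 91 days. Days 90 to 174, before the 6-month window opens, are 85 days, and 85/91 = 93%. This is a share of eligible calendar days, not a forecast of when offers were made. The window is counted to randomization, and an offer must come earlier. Someone randomized on days 175 to 180 may therefore also have been discontinued before the 6-month contact.

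**3. Follow-up lost per leaver.** Assume entry is uniform over the 91 days. The mean loss up to day 175 is (1 + 2 + … + 85)/91 = 3655/91 = 40.2 days.

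**4. Share of a group's person-time.** Lost share = k × 40.2/(5000 × 175), where k is the number leaving from one boosted group. The documents do not give k, so a range is shown:

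| k (assumed) | Share of 5000 | 6-month person-time lost |
|---|---|---|
| 150 | 3% | 0.7% |
| 300 | 6% | 1.4% |
| 600 (upper bound) | 12% | 2.8% |

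**5. Effect on detection.** Suppose, pessimistically, that leavers contribute nothing.

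| n remaining | p = 0.01% | p = 0.05% | p = 0.1% |
|---|---|---|---|
| 5000 | 0.394 | 0.918 | 0.993 |
| 4850 | 0.384 | 0.912 | 0.992 |
| 4700 | 0.375 | 0.905 | 0.991 |
| 4400 | 0.356 | 0.889 | 0.988 |

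Steps 4 and 5 count only people who enroll in Cohort 2. Decliners come on top, and the documents put no limit on their number.

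**6. Who is exposed.** Section 2.2.1 gives a data cutoff of 05 October 2021 with median follow-up of 2.5 months, counted from 7 days after the dose. That puts the median original booster at about 14 to 21 July 2021, and day 175 at about 5 to 12 January 2022. Section 10.7.9.4 says all participants had reached 2 months of blinded follow-up at the first interim analysis. If that analysis used the same cutoff, the last original boosters were given about 5 August 2021. Omicron was reported on 24 November 2021 (Section 10.10.2.1). By then the last-boosted were at about day 111 and the median at about day 126 to 133. Placebo recipients boosted later at Visit 101 would have been earlier in the window, so they are probably the more exposed group. These dates are inferences; the text at hand gives no enrollment dates for Substudy D.

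**The case against.** The strongest reply is that this is loose wording in a paragraph about early termination. No visit procedure implements it, and any collection schedule is subject to discontinuation. The protocol text at hand also ends within Section 10.10.2.1, so Substudy D's eligibility and procedure sections (10.10.5 and 10.10.8.6), where transfer might be handled, could not be checked. Part of this stands: the documents do not show that decliners were in fact dropped. But the rule appears twice in mandatory form. Unlike an ordinary withdrawal, it is a planned sponsor action that ends follow-up in people willing to continue.

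Several stronger readings are tempting and are not supported:

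- A reader might infer that 93% of offers came before the 6-month contact, or that originally boosted participants lost 85 to 99 days through offers at day 90. The first takes calendar days for offers; the second does not fit the dates in step 6.
- A reader might infer that SAEs in those who join Substudy D are lost. Section 8.3.1 collects them there from consent through Visit 405. The limitation is that they follow a fourth dose and that Section 9.3.1 has each substudy reported on its own.
- A reader might infer damage to the efficacy results. Primary and secondary efficacy use blinded follow-up only (Section 10.7.3), and the substudy was unblinded after the first interim analysis (Section 10.7.9.4). Only the exploratory incidence summary in Section 10.7.9.3.4 is shortened.
- A reader might infer that the healthiest people are removed. Substudy A already required healthy participants, and nothing ties offers to health. The only selection visible is age 18 to 55.
- A reader might infer that leavers are analyzed as followed to 6 months. Section 10.7.9.3.2 plans percentages and the safety population is everyone dosed, but handling of exposure may be set in the SAP, which is not at hand.

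**Conclusion.** The point holds as an inconsistency that touches a primary safety objective, and its size is modest. Discontinuation on offer cannot be squared with SAE collection to 6 months for people who are offered a later study and decline. The 6-month SAE record within Substudy A is also cut short for those who transfer before day 175. By enrollment alone, at most 600 of 5000 in one boosted group are affected. That is about 2.8% of the group's 6-month person-time, and detection at a 0.1% rate moves only from 0.993 to 0.988. The number of decliners is unknown and could add to this.

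The figures assume uniform entry over days 90 to 180 and, at the upper bound, that all of Cohort 2 comes from one boosted group. The conclusion also takes Substudy D to be a future study within the program. That is the natural reading, but the protocol does not say so expressly.

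**What to change.** Reconcile the passages:

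1. In Sections 1.1 and 10.7.4.1, make the trigger actual enrollment in the later study: *enrolled in* in place of *offered the possibility to participate in*. Decliners then stay in Substudy A through Visit 3 or Visit 103, with COVID-19 surveillance as already scheduled.
2. For those who transfer, state that Substudy A SAE follow-up ends at the next study dose. Cohort 2 already records the prior study and participant number at Visit 401 (Section 10.10.1.3.2), so the records can be linked.
3. Beside the 6-month SAE percentages, report how many left before day 175 after the booster, separately for the originally boosted and the crossed-over placebo recipients.

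The cost is a one-line change in two places and one added summary. The downside is continued contact with decliners, which the schedule already provides for. If follow-up is largely complete, the third item can still be done.
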